#### **1.1.7. V.A.C.ULTA™ Negative Pressure Wound Therapy System**

The V.A.C.ULTA™ Negative Pressure Wound Therapy System offers two methods of therapy. The therapy unit delivers both V.A.C.® Therapy (V.A.C.ULTA™ Therapy without instillation) and V.A.C. VERAFL™ Therapy (V.A.C.ULTA™ with instillation).

The SENSAT.R.A.C.™ Dressing/Technology allows egress of fluid from the wound bed, measures pressure at the wound site, and connects the dressing to the canister tubing.

An exudate canister attaches to the side of the therapy unit and holds the wound and instillation fluid collected from the wound bed.

The V.A.C. VERAFL™ Therapy option allows for NPWT and instillation of topical wound solutions. The VERAFL™ Therapy cycle is comprised of an instillation period, a solution dwell or soak period, and an NP period. The user programs the volume of solution to be delivered to the wound bed, the length of time the solution will be allowed to dwell in the wound, and the length of time NP will be applied before the instillation cycle repeats.

V.A.C. VERAFL™ Therapy using the V.A.C.ULTA™ Negative Pressure Wound Therapy System also includes (Table 1):

- An instillation cassette (V.A.C. VERALINK™ Cassette) connects a solution bag/bottle and the dressing tubing to the therapy unit. The cassette holds and delivers user-provided wound solutions to the wound bed via the automated volumetric pump.
- The V.A.C. VERAT.R.A.C.™ Pad incorporates tubing for fluid input, exudate/fluid removal, as well as pressure sensing at the wound site.

- The V.A.C. VERAFL0 CLEANSE CHOICE™ Dressing Kit contains VFCC, which is similar to the V.A.C.® GRANUFOAM™ Dressing but is less hydrophobic for enhanced fluid distribution. VFCC also has improved mechanical properties, including a higher tensile strength. The V.A.C. VERAFL0 CLEANSE CHOICE™ Dressing Kit also contains a polyurethane drape (V.A.C.® Advance Drape) with acrylic adhesive, a V.A.C. VERAT.R.A.C.™ Pad, a ruler and 3M™ Cavilon™ No Sting Barrier Film.
- Disposable canisters for the collection of wound exudate are available in three sizes: 300 mL, 500 mL, and 1000 mL. For this study, the 1000-mL canisters will be provided due to instillation.

Table 1: V.A.C.ULTA™ Therapy and V.A.C. VERAFL0 CLEANSE CHOICE™ Dressing Kit components.

Name/Description	Picture/Diagram
V.A.C.ULTA™ Therapy Unit	
Exudate Canisters Single-patient use, disposable canister (1000 mL).	
Instillation Cassette (V.A.C. VERALINK™ Cassette) Single patient use, disposable cassette with a spike.	
V.A.C. VERAFL0 CLEANSE CHOICE™ Dressing Kit For Subjects in the V.A.C.ULTA™ Therapy with instillation Treatment arm only. Contains: V.A.C. VERAFL0 CLEANSE CHOICE™ Dressing; V.A.C.® Advanced Drape; V.A.C. VERAT.R.A.C.™ Pad; Ruler; Cavilon™ No Sting Barrier	

## 2. STUDY OBJECTIVES

The primary objective of this study is to compare the short-term effects of the V.A.C.ULTA™ Negative Pressure Wound Therapy System with instillation therapy using normal saline and V.A.C. VERAFL0 CLEANSE CHOICE™ Dressing to collagenase ointment in wounds (eg, chronic, acute, traumatic, or dehisced wounds) and/or ulcers (ie, full-thickness wounds).

### 3. STUDY DESIGN

#### 3.1. Design Summary

ACCELERATE Study Schema										
Up to 10 Days	Day 0	Day 1	Day 2	Day 3	Day 4	Day 5	Day 6	Day 7	Day 8	Day 9
SCREENING	RANDOMIZATION 1:1	Collagenase Ointment Treatment Daily treatment for 6-9 days								
		VFCC and NPWTi-d Treatment Total treatment 6-9 days								
		First change								
		Second change								
		End of Treatment								

This randomized, controlled, prospective multicenter study will enroll Subjects diagnosed with wounds (eg, chronic, acute, traumatic, or dehisced wounds) and/or ulcers (ie, full-thickness wounds) that measure  $\geq 16 \text{ cm}^2$  of total surface area, have a minimum width of 2 cm (excluding undermining) before sharp and/or mechanical removal of eschar at the bedside, and are  $< 20 \text{ cm}$  across (edge-to-edge) at any point perpendicular to the wound edges. Subjects will receive either VFCC and NPWTi-d (V.A.C. VERAFLTM Therapy with saline solution) or collagenase ointment to manage their wound over a 6-9-day period. Bedside sharp and/or mechanical debridement procedures will be performed to remove eschar before randomization; however, sharp or mechanical debridement will not be performed after randomization during the treatment phase of the study period (up to 9 days).

For the purposes of this study, we will define and assess viable tissue. Viable tissue will not include the following: non-viable tissue, which can be loose or firmly adherent, hard, soft, dry, or wet. Slough is defined as a type of non-viable fibrinous tissue that consists of fibrin, pus, and proteinaceous material, and could be yellow, white, tan, gray, or green in appearance.

The study will randomize approximately 60 Subjects from approximately 15 sites in a 1:1 ratio to either the VFCC (ie, Treatment) arm or the collagenase ointment (ie, Control) arm after obtaining informed consent, undergoing screening procedures, and meeting all the inclusion criteria and none of the exclusion criteria.

### **3.1.1. V.A.C. VERAFL® CLEANSE CHOICE™ Dressing**

VFCC dressing will be applied to the wound bed and covered with drape material, providing a sealed environment for the application of NPWTi-d for a duration of 6-9 days. The dressing will be applied on Day 0 and changed twice during the treatment period, allowing at least 48 hours between each dressing change. The first dressing change will occur on Day 2-3, and the second dressing change will occur on Day 4-6. The dressing will be removed on Day 6-9 at the treatment endpoint.

### **3.1.2. Collagenase Ointment**

Collagenase ointment will be used as the control for this study as it is a commonly used option for wound cleansing. After application of the ointment, the wound will be covered with a compatible standard-of-care (SOC) dressing for up to nine (9) days. During this treatment period, the ointment can be reapplied once daily (or more frequently if the dressing requires replacement).

### **3.1.3. Duration of Study Participation**

The duration of study participation for each Subject is as follows:

- Screening Period: up to 10 days (Day -10 to Day 0)
- Treatment Period: up to nine (9) days (Day 0 to Day 9)

The maximum participation duration per Subject is up to 19 days.

## **3.2. Primary Endpoint**

The percent change in the wound bed surface area (cm^2) considered to be clean, healthy, and viable from baseline to Day 6-9 upon the final dressing removal.

### 3.3. Secondary Endpoints

The secondary endpoints are as follows:

- Percent change in total wound volume (cm^3) from baseline to Day 6-9 upon the final dressing removal
- Percent change in total wound area (cm^2) from baseline to Day 6-9 upon the final dressing removal
- Physician assessment of the need for surgical debridement upon completion of study treatment up to Day 6-9

### 3.4. Exploratory Endpoints

The exploratory endpoints are as follows:

- The absolute change from baseline to Day 6-9 upon the final dressing removal in the wound bed surface area (cm^2) considered to be clean, healthy, and viable, in the total wound area, and in the total wound volume
- The percent change and absolute change of granulation tissue from baseline to Day 6-9 upon the final dressing removal
- Number of treatment applications and/or dressing changes per Subject (ie, collagenase ointment applications versus VFCC applications)
- Total time to perform treatment applications and/or dressing changes per Subject

In addition to these exploratory endpoints, the following data will be collected from Subjects in one of the groups:

- Total number of collagenase ointment tubes used per Subject
- Number of blockage and leak alarms (obtained from the V.A.C.ULTA™ Therapy Unit log)

Additional exploratory endpoints may be added and will be detailed in the statistical analysis plan (SAP).

### 3.5. Safety Endpoint

The safety endpoint is the Subject incidence of adverse event(s) (AEs).

## 4. STUDY PROCEDURES AND ASSESSMENTS

### 4.1. Informed Consent

The Investigator, or designee, will discuss the purpose of this study with potential Subjects or their legally authorized representative if the Subject is unable to provide their own informed consent. Each individual will review the Informed Consent Form (ICF) approved by the local Institutional Review Board (IRB). The ICF must be signed according to IRB requirements before the Subject can undergo any study-related procedures. Informed consent will be obtained under these conditions:

- Subjects or their legally authorized representatives must be made aware of the purpose of the study and the potential risks and benefits known or that can be reasonably predicted or expected.
- Subjects or their legally authorized representatives must be given the opportunity to ask the Investigator questions and must be provided time to consider participation in the study.
- ICFs will be written in a manner that is non-technical and understandable to the Subject or their legally authorized representative.
- Subjects or their legally authorized representatives will not be led to believe that they are waiving their legal rights to release the Investigator, KCI®, the study site, or any of their agents from liability for negligence.
- Subjects or their legally authorized representatives will be asked to sign and date the ICF indicating their informed consent to participate in the study.
- The Investigator's responsibilities during the ICF process include:

- screening out potential Subjects who may not be able or willing to comply with the study protocol.
- ensuring that Subjects or their legally authorized representatives have signed the ICF prior to undergoing any study-related assessments.
- ensuring that each Subject or their legally authorized representative receives a copy of the signed ICF.

## **4.2. Inclusion/Exclusion**

In order to be considered for randomization, a Subject must meet all eligibility criteria and be assessed no more than 10 days prior to the treatment application. Subjects who do not meet all eligibility criteria will not be eligible for randomization, will discontinue from the study, and will be considered a screen failure. Inclusion and exclusion criteria will be reconfirmed immediately prior to randomization if Visit 1 and Visit 2 are on different dates.

### **4.2.1. *Inclusion Criteria***

The Subject:

1. is anticipated to be hospitalized for the duration of treatment (minimum of 6 days).
2. is  $\geq 18$  years of age.
3. or their legally authorized representative is able to provide informed consent.
4. has been diagnosed with a wound (eg, chronic, acute, traumatic, or dehisced wounds) and/or ulcer (ie, full-thickness wounds) that meets the following criteria:
  - a) total surface area measuring  $\geq 16 \text{ cm}^2$ , including a minimum width of 2 cm (before removal of eschar at the bedside and excluding undermining).
  - b)  $< 20 \text{ cm}$  across (edge-to-edge) at any point perpendicular to the wound edges.
5. has, in the opinion of the investigator, no more than 2/3 of the wound bed surface area considered to be clean, healthy, and viable. If eschar is present at baseline, it must be removed by bedside debridement prior to assessing the percentage of

clean, healthy, and viable wound bed.

6. has a negative urine or serum pregnancy test at screening (if female and has potential for pregnancy) and is willing to take precautionary measures to prevent pregnancy during the duration of the study (up to 9 days).

#### **4.2.2. *Exclusion Criteria***

The Subject:

1. has been diagnosed with malignancy in the wound.
2. has untreated osteomyelitis.
3. has an untreated systemic infection.
4. has active cellulitis in the periwound area.
5. has a known allergy or hypersensitivity to study materials: collagenase ointment, dressing(s), and/or dressing components such as acrylic adhesives or polyurethane.
6. has, in the opinion of the investigator, a clinically significant condition that would impair the Subject's ability to comply with the study procedures.
7. has had radiation directly to the wound area.
8. has been diagnosed with a major vascular deficit limiting arterial inflow to the wound region, as determined by the Investigator's interpretation of the Subject's medical history.
9. has eschar in the wound that cannot be removed by bedside sharp and/or mechanical debridement.
10. is participating in another interventional clinical trial for the duration of the study.
11. has unexplored fistulas in the wound or fistulas in the wound that connect to other body cavities.
12. has a wound with any tunneling present.

13. has inadequate hemostasis at the wound site, as determined by the investigator.

#### **4.3. Premature Study Termination**

If the study is terminated prematurely or suspended, study Subjects and the IRB will be informed promptly and provided with the reason(s) for the termination or suspension by KCI® or by the Investigator. If applicable, regulatory authorities and the personal physicians of the Subjects will also be informed.

##### **4.3.1. *By Sponsor***

KCI® reserves the right to discontinue the clinical study for business or ethical reasons at any time, such as, but not limited to:

- Information regarding the study product causes doubt as to the benefit/risk ratio.
- Changes in medical practice limit utility of the data obtained from the study.

KCI® reserves the right to terminate a study at a site at any time, including but not limited to, any of the following reasons:

- Investigator(s) lack of compliance with the approved study protocol and/or applicable regulatory or IRB guidelines in conducting the study
- Incidence or severity of AEs indicates a potential health hazard or poses an unreasonable risk to the study participants
- Subject enrollment is unsatisfactory
- Fraud or misconduct

##### **4.3.2. *By IRB***

The IRB may choose to discontinue the study at the site for which they granted approval. If the IRB discontinues the study, the Investigator will report a withdrawal of IRB approval to KCI® within five (5) working days.

## 4.4. Subject Withdrawal or Termination

### 4.4.1. *Reasons for Withdrawal or Termination*

Subjects may withdraw from participation in the study at any time upon request.

The Investigator may choose to terminate the participation of a Subject from the study with or without their consent for any of the following reasons:

- Adverse events
- Noncompliance
- For any reason that may, in the opinion of the Investigator, negatively affect the safety or well-being of the Subject

### 4.4.2. *Handling of Withdrawal or Termination*

Every effort should be made to complete wound and AE assessments prior to the Subject withdrawal.

For Subjects who are lost to follow-up, the Investigator will make attempts to collect at least the vital status (eg, whether the Subject is alive) before formally withdrawing the Subject from the study. Prior to considering a Subject lost to follow-up, at least two documented attempts should be made to contact the Subject through all available routes, and a certified letter should be sent to the permanent address on file.

Once the Subject withdraws from the study, no further study evaluations will be performed, and no additional data will be collected. The Investigator may retain and continue to use any data collected before withdrawal. The Subject will not be replaced.

If, for any reason, the Subject is withdrawn by the Investigator from this study, the Investigator will inform the Subject and KCI™.

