### **4.13. Treatment Removal**

#### **4.13.1. V.A.C. VERAFL0 CLEANSE CHOICE™ Dressing**

Subjects will remain hospitalized and on Study Treatment therapy for two (2) dressing changes (ie, 6 to 9 days). Dressing removal should not occur prior to 48 hours from the previous dressing change unless a replacement is required to maintain therapy. The Investigator may then use their wound treatment of preference to ensure the continuation of wound care. The date and time of dressing removal will be documented.

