#### **4.17. End of Study**

The following information will be documented:

- Last day of study participation
- Completion status – Did Subject complete the study (ie, 6-9 days of therapy)?
- Reason for study discontinuation

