### **5.2.5. Unscheduled Visits**

Outside of scheduled study visits, if the Subject needs to be assessed by the Investigator or a medically licensed sub-investigator for any reason, the following procedures and assessments will be performed and documented in the Subject's medical records/source notes:

- Wound assessment

- Dressing change
- Dressing removal, if Subject is withdrawn early
- 3D imaging
- End of study, if Subject is withdrawn early
- Concomitant medications
- AE assessment and SAE reporting

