5.4. Modified Intention-to-Treat Population (mITT)

Modified intent-to-treat (mITT) will include all randomized Subjects with the following:

- i. met all the inclusion criteria and none of the exclusion criteria,
- ii. had no more than 2/3 of the wound bed surface area considered to be clean, healthy, viable wound bed as determined at the baseline measurement confirmed with 3D images by an independent assessor,
- iii. received either the V.A.C. VERAFL0 CLEANSE CHOICE™ Dressing and NPWTi-d or collagenase ointment,
- iv. had the primary endpoint assessment on Day 6-9

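### Protocol 4.4 does not separate stopping study treatment from leaving the study, so a subject who exits before Day 6 is lost to the primary analysis

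*Protocol*

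**What the plan says.** - **Ending participation.** Protocol 4.4.1: "The Investigator may choose to terminate the participation of a Subject from the study with or without their consent". The reasons listed are adverse events, noncompliance, and anything the investigator judges harmful to safety or well-being.
- **After exit.** Protocol 4.4.2 covers withdrawal and termination under one heading: "Once the Subject withdraws from the study, no further study evaluations will be performed, and no additional data will be collected". Its last paragraph speaks of subjects withdrawn by the investigator, so the rule does not read as limited to withdrawal of consent.
- **At exit.** The same section opens with "Every effort should be made to complete wound and AE assessments prior to the Subject withdrawal". Protocol 5.2.5 lists 3D imaging at unscheduled visits, along with "Dressing removal, if Subject is withdrawn early".
- **Completion.** Protocol 4.17 equates completing the study with 6 to 9 days of therapy.
- **Primary analysis set.** One condition for the mITT set (Protocol 8.2; SAP 5.4, item iv) is that the subject "had the primary endpoint assessment on Day 6-9". SAP 8.1 makes mITT the primary set, and SAP 6.3.1 rules out imputation in it.
- **Supportive analyses.** SAP 8.1 repeats the primary model on the FAS, with post-baseline gaps filled by last observation carried forward, and on the Per-Protocol set.

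**The concern.** Study treatment lasts only 6 to 9 days and the primary endpoint is read at its end, so any exit before Day 6 removes the endpoint. The permitted reasons for termination can be tied to how the wound is doing. Protocol section 6 lists stalled healing and wound deterioration among the NPWTi-d/VFCC risks, and the collagenase risk list differs. Sites know the assigned arm (SAP 3.4), so termination decisions are made with that knowledge. If the subjects lost are disproportionately those doing badly, and more come from one arm, the mITT comparison becomes one of completers. An image that was never taken cannot be recovered at the analysis stage.

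**Working it through.** **1. Follow one subject.** Suppose participation ends on Day 4 for an adverse event.
- Protocol 4.4.2: an exit wound assessment is attempted, then nothing further is collected.
- SAP 5.4 item iv: an exit image on Day 4 is not a Day 6-9 assessment, so the subject is outside the mITT. Protocol 8.1.1 computes the endpoint from the final post-baseline value, which might seem to admit an exit image, but item iv still excludes the subject.
- SAP 6.3.1: no imputation in the primary analysis.
- SAP 8.1: the subject reappears in the supportive FAS with the Day 4 value carried forward, which assumes no change afterwards.

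A subject terminated within Day 6-9 who has an exit image could still qualify.

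**2. Reproduce the plan's sample size** (Protocol 8.4.1: means 20 and 40, SD 22; two-sided 0.05, 80% power; rank-sum test). With Noether's formula:
- p = Φ(20 / (22√2)) = 0.7398
- n = (1.960 + 0.842)² / [6 × (0.7398 − 0.5)²] = 22.74, so 23 per arm, with power 80.4% at 23
- Non-evaluable allowance: 1 − 46/60 = 23.3%, or 30 − 23 = 7 per arm

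The plan's figures are confirmed. The allowance is described as covering wounds that the independent assessor finds more than 2/3 viable, plus loss to follow-up. It protects precision and does nothing about bias. Seven per arm is used below only as an upper reference point, not as an expected number of terminations.

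**3. Arithmetic range.** Assume k of 30 VFCC subjects are lost, retained VFCC subjects average 40, control is complete at 20, and the lost subjects would have averaged m. The mITT difference of 20 then overstates the all-randomised difference by k × (40 − m)/30.

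| k | m = 20 | m = 0 | m = −20 |
|---|---|---|---|
| 1 | 0.7 | 1.3 | 2.0 |
| 3 | 2.0 | 4.0 | 6.0 |
| 7 | 4.7 | 9.3 | 14.0 |

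**4. Simulation with no true difference** (40,000 trials per case, 30 per arm, SD 22, two-sample t-test at the protocol's final level of 0.048). Moderate means that the exclusion score correlates about 0.5 with outcome. Extreme means that the worst outcomes are always the ones lost.

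| Lost VFCC / control | Link to outcome | Shift in difference | Two-sided type I error |
|---|---|---|---|
| 7 / 0 | none | −0.1 | 4.9% |
| 3 / 0 | moderate | +2.0 | 6.4% |
| 7 / 0 | moderate | +4.3 | 10.7% |
| 3 / 0 | extreme | +4.1 | 12% |
| 7 / 0 | extreme | +8.5 | 33% |
| 3 / 3 and 7 / 7 | moderate | 0.0 | 5.6% |
| 3 / 3 | extreme | about 0 | 7.8% |
| 7 / 7 | extreme | 0.0 | 10.4% |
| 0 / 7 | moderate | −4.2 | 10.5% |
| 0 / 7 | extreme | −8.5 | 33% |

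Equal loss leaves the difference unshifted, although the error rate still rises somewhat because dropping the lowest values understates the spread. Loss from control alone works against VFCC: with a true difference of 20, losing 7 control subjects gives an average estimate of 15.8 (moderate) or 11.5 (extreme). The simulation does not include the covariates of the SAP model.

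**The case against.** The best defence is that the protocol does not force anyone out. Section 4.4.1 is permissive, and nowhere does the protocol say that stopping treatment requires leaving the study. Section 8.1.2.3 defines an Incomplete Treatment outcome for under six days of therapy, and 8.3.5.3 tabulates every outcome in the mITT, whose members have a Day 6-9 assessment. Section 8.3.7 also names treatment/study discontinuation. So a reader might infer a ban on following subjects off treatment, but the text supports only an undrawn distinction. Likewise, a reader might infer that nothing is known about subjects who exit. In fact 4.4.2 and 5.2.5 provide for an exit assessment with imaging, so the carried-forward FAS value can be an end-of-treatment image, and Protocol 7.7 follows ongoing treatment-related adverse events for up to 30 days.

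A second objection concerns what a later image measures. The endpoint is read at final dressing removal. Once treatment ends, Protocol 4.13 lets the investigator choose further wound care, which could include debridement and so change viable area directly. Pooling such images unflagged would be an estimand choice open to debate.

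Both objections stand in part. The first narrows the defect to a missing distinction. The second governs how the extra images are used. Neither puts a subject who exits before Day 6 into the primary analysis.

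**Conclusion.** The point holds as a gap in data collection with an unknown effect. The documents give neither a withdrawal rate nor outcomes for those who leave, so neither the size nor the direction of bias can be stated. Under the assumptions shown, loss of 3 to 7 of 30 from the VFCC arm alone moves the difference by about 2 to 8.5 points in simulation, and by up to 14 in the most extreme arithmetic case, against a planned 20. The shift requires exits that are both related to outcome and unequal between arms.

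Three stronger readings are not supported:
- **That the bias favours VFCC.** Loss from control alone reverses it.
- **That the arms have known, distinct causes of stopping, such as device leaks or pain.** Leaks are not a listed reason for termination, Protocol 4.11.1 and 4.12.1 provide for extra drape and dressing replacement, and pain appears in the risk tables of both treatments.
- **That most subjects who exit are still inpatients.** Inclusion criterion 1 speaks only of anticipated hospitalisation. Section 4.13.1 says of the VFCC arm "Subjects will remain hospitalized and on Study Treatment therapy for two (2) dressing changes", but 4.13.2 does not repeat this for collagenase.

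The change is worth making because it is cheap and the data cannot be obtained later.

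**What to change.** The change concerns data collection and analysis only, not when treatment should stop.

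**Protocol 4.4**
- Distinguish discontinuing study treatment from withdrawing consent, and limit the stop on data collection to the latter.
- For subjects who discontinue treatment, still obtain the scheduled Day 6-9 3D image and adverse event assessment where they remain available.
- Record intervening wound care, including any debridement.

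**SAP**
- Prespecify a supportive analysis of randomised subjects that uses observed Day 6-9 values in place of carried-forward ones.
- Flag images taken after other wound care or debridement, and show results with and without them.
- State whether these subjects enter the mITT. If they also meet items i to iii, a Day 6-9 image would admit them as the set is now worded.

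**Reconcile**
- Protocol 4.4.2 with the 30-day adverse event follow-up in 7.7.
- The Incomplete Treatment category in Protocol 8.1.2.3 with SAP 8.2.5, which keeps only Yes and No.

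The cost is a protocol clarification, a short SAP addition and a few images on equipment supplied to the sites. The planned 23 evaluable subjects per arm is unaffected. The drawback is that some final images will reflect later wound care rather than the assigned treatment, which is why the flag and the paired results are needed.
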